#### Visit 1: (Approximately 40 minutes)

- Consent
- Oral hard and soft tissue examination
- Eligibility

- Patient assessment of standard mouth images with dentist to look at the appearance of healthy vs non- healthy mouths (See Appendix 3)
- Intra-oral scan of patient's mouth and assessment of plaque download report for patient to take away (Appendix 5)
- Plaque and gingival health assessments (See Appendix 4)
- Randomisation
- Completion of questionnaire with regards to current oral health/hygiene practices (Part A) and patients' attitudes to oral health (Part B) (See Appendix 1 Parts a and b)
- Provision of OHI instruction by dentist depending on randomisation either standard verbal OHI **or** enhanced OHI (pictorial + verbal OHI) with a detailed pictorial report for the patient
- Provision of OH leaflet and mouth mirror for participants use at home for those participants assigned to the pictorial + verbal OHI group only.

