#### Study Design

The study will be a parallel, randomised (1:1 ratio) 2 treatment, single centre study. The study sites will be the University of Bristol Dental School and Hospital including the South Bristol Community Hospital outreach centre, and the general dental practice Redland Park Dental Surgery. The study will be conducted by the Clinical Trials Unit team members who are part of Bristol Dental School.

At Visit 1, following provision of informed consent and confirmation of eligibility to take part in the study, participants will be provided with a questionnaire to complete regarding gum (gingival) health and then shown standard pictures of teeth and gingivae. They will be asked to indicate whether they think the pictures demonstrate oral health or oral disease and which they think represents their current oral health.

The participants will undergo an oral hard and soft tissue examination.

An intra-oral diagnostic camera will then be used by the clinician to take an intra-oral scan including images and a video of the patient's mouth. The images and video captured will be downloaded and a pictorial report prepared of their oral health. The camera software has the ability to detect plaque on the teeth and this will also be used to assess the levels of plaque present on the participant's teeth.

The study dentist will carry out a gum health examination (Modified Gingival Index, MGI) for the participant and will then measure the amount of plaque present using a traditional technique involving placing dye (food colouring) onto the surface of the teeth which highlights plaque (O'Leary et al 1972).

Participants will be randomised by study staff to one of 2 treatment groups (Control group - standard verbal oral health instructions (verbal OHI) or Test group – pictorial report + verbal oral health instructions (picture + verbal OHI) using a predetermined randomisation schedule.

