#### Secondary Objectives

- Patient perceptions of effectiveness of a having a pictorial report of their oral health as part of their dental care at Visit 1 and Visit 2
- Patient attitudes to oral health measured at Visit 1 and Visit 2
- Participants understanding of oral health vs oral disease at Visit 1 and Visit 2
- Assessment of the accuracy of the intra-oral camera's ability to assess plaque levels compared to the clinician using traditional techniques using dye

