# Appendix 1: Patient Questionnaires for Visit 1 Patient Oral Health Questionnaire- Visit 1 – Part A

If you have trouble completing this questionnaire, please ask a member of staff to assist you.

1.	What is your date of birth D D M M Y Y Y Y
2.	How old are you?
3.	identify my gender as
	Man
	Woman
	Prefer not to disclose
4.	How many times per day do you regularly brush your teeth? (Please tick one box only, Less than once a day
	Once a day
	Twice a day
	More than twice a day
5.	When do you normally brush your teeth? ( Please tick all that apply )
	In the morning
	in the evening
	During the day
6.	Did you usually brush your teeth (Please tick one box only)
	Before breakfast
	Neither before or after breakfast
	After breakfast
	Both before and after breakfast

7. Which kind of toothbrush did you use the most often? (*Please tick one box only*)

8. Are you right-handed or left-handed?

(Please tick one box only)

Right-handed	
Left handed	
Both	

9. Do you currently use a toothpaste?

YES	
NO	

If yes, which toothpaste do you currently use? \_\_\_\_

10.Do your gums bleed when you brush your teeth?

YES	
NO	
11.	Do you think you have bad breath?

Occasionally

12. Do you use any of the following additional teeth cleaning aids? (*examples are shown below, please tick the box next to any you have used or if you use none of these, tick none*)

14. Are you currently concerned about your oral health?

YES	
NO	

15. If yes, what are your concerns?

Condition of teeth	
Function of teeth	
Appearance	
Breath	
Sensitivity	
Other/Not sure	
None	

16. How would you rate your current oral health?

Excellent	
Very good	
Good	
Fair	
Poor	
Not sure	

17. Are you motivated in maintaining oral health?

Very motivated	
Fairly motivated	
Neither motivated or not motivated	
Not motivated	
Not sure	

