## Appendix 3: Standard Images of oral health and oral disease

Do the images below, in your opinion, show oral health or oral disease? Indicate which image you think represents your current oral health *Please 'tick' the box which represents your answer for each image* 

	IMAGE 1	IMAGE 2	IMAGE 3
Health			
Disease			
Do not know			
Represents my current oral health			

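### The image task that measures participants' understanding is described inconsistently, merges two questions on one form, and is not scheduled at Visit 2

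*Protocol*

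**What the plan says.** Understanding is a secondary objective, to be measured at both visits. The Secondary Objectives list under Outcomes has "Participants understanding of oral health vs oral disease at Visit 1 and Visit 2".

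The task is described in three places in the Protocol:

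- **Study Design** has participants look at standard pictures: "They will be asked to indicate whether they think the pictures demonstrate oral health or oral disease". They also say which picture matches their own mouth. No dentist is mentioned, and the step comes after eligibility is confirmed and before the mouth is examined.
- **The Visit 1 list** has "Patient assessment of standard mouth images with dentist to look at the appearance of healthy" versus non-healthy mouths, and points to Appendix 3. Here the step comes after the examination and the eligibility check, and before randomisation.
- **Appendix 3** asks the participant's opinion on whether each of three images shows health or disease, and then: "Indicate which image you think represents your current oral health". The answer grid has one column per image and four rows: Health, Disease, Do not know, and "Represents my current oral health". The instruction is "Please 'tick' the box which represents your answer for each image".

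The Visit 2 list contains questionnaires, a scan, plaque and gingival scores and the report, but no image task. Appendix 2 (the Visit 2 questionnaires) contains none either.

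**The concern.** The measure is meant to capture what participants can recognise for themselves. If one clinician hands over the form in silence and another talks through the pictures, the answers mean different things. A prompted answer cannot be turned back into an unprompted one at analysis. With only three images the scale is short, so even modest prompting at Visit 1 leaves less room to show a gain.

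The form has a separate weakness. Classifying an image and identifying with it are different questions, but they share a column and a singular tick instruction. A participant who takes the instruction literally has to choose between them. The classification most at risk is then that of the image closest to the participant's own mouth. A blank self-image row is also uninterpretable: it may mean that none of the images fits, or that the question was skipped.

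Finally, without a scheduled Visit 2 administration, change in understanding cannot be measured at all.

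**Working it through.** The Protocol gives no figure for this outcome, so there is nothing to reproduce. The check compares the sections and then counts.

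**1. Whose judgement is recorded?** Study Design and Appendix 3 both ask what the participant thinks. The Visit 1 line still calls the step the patient's assessment, but adds the dentist and a purpose of looking at healthy and unhealthy appearances. That wording fits a dentist who merely presents the pictures and equally a dentist who discusses them. No section says which, or that answers come before any comment.

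**2. When is it done?** Study Design: eligibility, pictures, examination. Visit 1 list: examination, eligibility, pictures. Both orders put the task before randomisation, so both arms do it in the same way.

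**3. Is there another measure of the objective?** Part A covers habits, concerns and self-rating. Part B covers attitudes and beliefs on a 1 to 10 scale. Only Appendix 3 asks participants to tell health from disease, so it is the only direct measure.

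**4. How many classifications could the form lose?**

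- Inputs: about 20 participants, 10 per arm (Randomisation); 3 images (Appendix 3).
- Classifications per administration: 20 × 3 = 60, or 10 × 3 = 30 per arm.
- Assumption: each participant identifies with exactly one image.
- If everyone ticks both a classification and the self-image row: 0 of 60 lost (0%).
- If everyone uses a single tick per image: 20 × 1 = 20 lost, and 20/60 = 33% (10/30 = 33% per arm).
- If half read it as a single tick: 10/60 = 17%.

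The Protocol does not say how participants will read the instruction, so the range is 0 to 33%. Several Part A items settle the matter explicitly, for example with "Please tick one box only". Appendix 3 carries no such rule in either direction.

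**5. Is the measure collected at both visits?** The objective names Visit 1 and Visit 2. The procedure lists provide it at Visit 1 only.

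**The case against.** The strongest reply is that all three descriptions keep the judgement with the participant, and that mentioning the dentist may mean no more than who shows the pictures. That is a fair reading. The Protocol does not say that the dentist explains, corrects or gives answers. What stands is that the wording permits it and no safeguard excludes it.

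Three stronger readings are tempting, and the documents do not support them:

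- **The form allows one tick per image, so a third of the answers are lost.** The instruction is ambiguous rather than restrictive. The fourth row plainly answers the second question, and a participant can tick twice. The 33% is an upper bound.
- **The score starts at its ceiling and cannot show a gain.** One could set guessing, 3 × 0.5 = 1.5 correct, against 3 of 3 after full prompting. Both values are assumed: the first ignores the Do not know option and any prior knowledge, and the second supposes complete coaching. Only the direction is supported: prompting would raise baseline scores and shrink the room for improvement.
- **Controls receive part of the picture intervention, which narrows the plaque and gum-health contrast.** The task is identical in both arms and precedes randomisation. The test intervention is the participant's own images, explained, with a report, leaflet and mirror; three generic pictures do not deliver that. Some common dilution is conceivable, but its size is unknown and nothing in the Protocol demonstrates it.

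It can also be said that this is one secondary objective in an estimation pilot of about 20 people. That is right, and it sets the priority.

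**Conclusion.** The point holds as a matter of measurement quality for one secondary objective. The Protocol gives no single rule for how or when the image task is done, the form merges two questions, and Visit 2 omits a measure that the objective requires.

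The possible loss of classifications is 0 to 20 of 60 per administration (0 to 33%), assuming that each participant identifies with one image. Any prompting would raise baseline understanding and reduce the scope to show a gain, by an amount that the documents do not allow one to estimate. It would not favour one arm. The Visit 2 omission is the firmest element because it needs no assumption about behaviour: as listed, no change in understanding can be calculated. The priority is minor, but the change is worth making before recruitment because neither prompted nor missing answers can be recovered later.

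**What to change.** 1. **Visit 1 list.** State that, once eligibility is confirmed, the participant completes Appendix 3 unaided and before any discussion of oral findings, and that staff give no answers on the standard images until the Visit 2 assessments are complete. Bring the order in Study Design into line. Placing the task after eligibility avoids a conflict with the Inclusion Criteria, which need a gingival score and hence a look in the mouth.
2. **Appendix 3.** Split it into two questions. A: for each image, tick one of Health, Disease or Do not know. B: which image is most like your mouth (1, 2, 3, none of these, not sure). With a full response to A, the loss described above falls to 0 of 60, and B separates a considered none from a skipped question.
3. **Visit 2 list.** Add the same unaided task, before any pictorial report is reviewed with the participant.

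The cost is a few lines in the visit lists and Study Design and a one-page form edit. Participants wait until Visit 2 to learn the answers, and Visit 2 becomes slightly longer.

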# Project proposal

**Title** A proof of principle study to evaluate the provision of a pictorial report following dental oral hygiene instruction to aid participants improving their gum health over a 4-week period

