#### Aims

The aim of this study is to estimate the effectiveness of the provision of patient specific oral hygiene instruction (OHI) with the use of a pictorial report following consultation with a dentist compared to standard verbally provided oral hygiene instruction with regards to patient plaque levels and improved gingival health, over a four-week period.

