#### Primary Objectives

• To compare patient plaque levels and gingival health following the provision of enhanced OHI with a detailed pictorial report for the patient vs. the use of standard verbal OHI instructions alone over a 4-week period.

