The images captured will be downloaded and form a pictorial report of the health of the patient's mouth which will be provided to the patient. For those participants allocated to receive the pictorial report + verbal OHI (test group), the images and video captured will be explained to the patient so they can understand their current oral health. Participants assigned to receive standard verbal OHI alone will not be shown or have a review of the images collected by the intra-oral camera or be provided with a pictorial report of their current oral hygiene at Visit 1, however they will receive this at the end of the study.

For all participants, oral hygiene instruction will then be provided by a single dental clinician. This will be a different clinician from the clinician performing the dental assessments and scans of the mouth. For participants assigned to receive the pictorial report + verbal OHI (test group), they will be provided with oral hygiene instruction, a leaflet on oral health and a mouth mirror to use at home.

Participants will also receive questionnaires on their current oral hygiene practices and attitudes to oral health.

An appointment will be made for the patient to return to the study site in 4 weeks and they will be assessed for plaque levels and gingival health and a further scan of their mouth taken. For those participants assigned to receive the pictorial + verbal OHI, a pictorial report will be generated and reviewed alongside their initial report with the patient and advice provided for ongoing oral health maintenance.

For those participants who were assigned to receive standard verbal OHI alone, following the completion of study assessments at Visit 2, the dental clinician will then review the images of their mouth captured at both Visit 1 and Visit 2 and provide the patient with a copy of their pictorial report from both Visits to take away with them. These participants will also be provided with a mouth mirror and an information leaflet regarding the importance of maintaining good oral health along with advice for their individual ongoing oral health maintenance.

For each patient recruited to the study, they will be required to attend 2 study visits with the research team. The appointments are as outlined below:

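### The leaflet and mouth mirror go to the test arm only during the four weeks, so the trial estimates the effect of a package and cannot attribute a difference to the pictorial report.

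*Protocol*

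**What the plan says.** The Protocol describes the intervention in these places, and none mentions a leaflet or a mirror:

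- Title: "A proof of principle study to evaluate the provision of a pictorial report following dental oral hygiene instruction".
- Aims: "patient specific oral hygiene instruction (OHI) with the use of a pictorial report following consultation with a dentist compared to standard verbally provided oral hygiene".
- Primary Objectives: "enhanced OHI with a detailed pictorial report for the patient vs. the use of standard verbal OHI instructions alone over a 4-week period".
- Study Design, arm label: "Test group – pictorial report + verbal oral health instructions (picture + verbal OHI"; the control label is standard verbal instruction.
- Outcomes (Primary Objectives) and Expected outcomes: the report together with tailored OHI.

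What is handed out is set in other places. The Visit 1 list has this entry: "Provision of OH leaflet and mouth mirror for participants use at home for those participants assigned to the pictorial + verbal OHI group only". Study Design agrees, and says of the controls, once their Visit 2 assessments are done: "These participants will also be provided with a mouth mirror and an information leaflet". The Visit 2 list and the section on items provided to the patient also defer these items for controls. The latter places them after all study assessments and lists report, leaflet and mirror as three separate items.

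**The concern.** A reader of the title or arm labels would take the trial to compare verbal instruction with and without a pictorial report. As run, the test arm also has written oral health information and a mirror for home use for the whole period over which plaque, gingival index and bleeding are compared. Either could plausibly affect plaque removal by itself; the Protocol gives no evidence either way.

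At stake is the sentence that can be written at the end. A favourable difference would naturally be reported as an effect of the camera-based report, and Expected outcomes already credits the report with tailored instruction. The design does not support crediting the report separately from the items handed out with it. That matters for a proof-of-principle study whose result may decide whether the report is worth testing further.

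**Working it through.** The Protocol gives no figure for this point, so the check sets side by side what each arm holds between Visit 1 and the Visit 2 assessments.

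| Component | Test arm | Control arm | Named in title, Aims, Primary Objectives or arm label? |
|---|---|---|---|
| Verbal OHI | yes | yes | yes |
| Pictorial report and explanation | yes | after Visit 2 assessments | report yes |
| Tailoring of OHI | possibly | at Visit 2 | yes in Aims (patient-specific); Primary Objectives says enhanced |
| Leaflet | yes | after Visit 2 assessments | no |
| Home-use mirror | yes | after Visit 2 assessments | no |

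**Outcome window.** Outcomes defines change from Visit 1 to Visit 2 (week 4). The control arm's deferred items therefore arrive after the last measurement and cannot influence it.

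**What the model estimates.** Statistical Analyses specifies a random effect for participant, one fixed effect for treatment, and adjustment for covariates such as age and gender. Let R be the effect of the report with its explanation, L that of the leaflet, M that of the mirror and T that of any tailoring. Ignoring interactions,

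expected difference in change = R + L + M + T.

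This is one estimable quantity and up to four unknowns. The indicators for report, leaflet and mirror are the same column of data: 1 for all 10 test participants and 0 for all 10 controls. Adding them as separate terms would leave the model unidentified. More participants or more covariates would not help, because the columns would remain identical.

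**Range of attribution.** The Sample Size section uses 0.69 as an example difference in change in plaque score. Let s be the share due to everything other than the report. With additive effects and no component doing harm, R = 0.69 × (1 − s):

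- s = 0: 0.69
- s = 0.25: 0.5175
- s = 0.50: 0.345
- s = 0.75: 0.1725
- s = 1: 0

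The data would look the same in all five cases. The Protocol gives no basis for choosing s, so this is a range under an assumption and not an estimate of bias.

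**Other sources of separation.** There is no third arm and no factorial element. The Visit 2 questionnaire (Part A, items 10 and 11) asks whether the report was useful and how often it was consulted. The questionnaire text available has no item on use of the leaflet or mirror, so even a descriptive comparison of the components is not possible.

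**The case against.** The strongest reply is that this is a deliberate package. Aims and Primary Objectives do not offer a bare contrast of report against no report; they speak of patient-specific or enhanced instruction with a report, and Outcomes adds tailoring. Comparing an enhanced education package with standard verbal instruction is a legitimate design. Its allocation is stated openly and consistently, controls receive everything in the end, and isolating components is not a listed objective. This largely stands. It does not remove the point, because even the broadest of these descriptions omits the leaflet and mirror. The Visit 1 list itself explains enhanced OHI as pictorial plus verbal and puts the leaflet and mirror in a separate entry.

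Four stronger readings might be inferred, and the documents do not support them:

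- *The randomised comparison is invalid.* It is not; it estimates the effect of the package as delivered.
- *The proof of principle goes unanswered.* That is too strong. Sample Size presents this as a 20-person pilot for estimation, and a package result still informs whether to proceed. The secondary objectives on perceptions of the report and on camera accuracy do not depend on this contrast, and the questionnaire gives some descriptive information specific to the report.
- *Tailored instruction is a hidden extra.* It is declared in Aims and Outcomes. What remains unclear is whether the verbal content differs between arms, since in the arm labels the word standard qualifies only the control.
- *The leaflet and mirror produce a bias of a particular size.* No document gives one.

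**Conclusion.** The point holds as a matter of attribution. During the four weeks the report, leaflet and mirror are completely aliased, possibly together with tailored instruction, while the title, Aims, Primary Objectives, arm labels and Expected outcomes leave out the leaflet and mirror. The treatment effect is valid for the package and cannot be assigned to the report. The report's share is unidentified: between none and all of any observed benefit if no component does harm, and not even bounded in that way otherwise. This conclusion rests only on the allocation stated in Study Design, Visit 1, Visit 2 and the items section, and on the two-arm model. It needs no assumption about how effective a leaflet or a mirror is. It should be settled before the results are interpreted, but it is not a failure of the randomised design.

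**What to change.** **Preferred: define the package.** In the title, Aims, Primary Objectives, Study Design arm labels, Outcomes and Expected outcomes, describe the test intervention as the pictorial report with its explanation, the leaflet and the home-use mirror, with any tailoring of the instruction stated. Limit the conclusion to that package. The cost is text only; conduct, materials and sample size are unchanged. The trial gives up a claim about the report alone, which the present design cannot support in any case.

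**Alternative, if the report itself is the target.** Give the leaflet and mirror to both arms at Visit 1, and state whether the verbal OHI content is the same in both. If it is the same, the arms differ only by the report and its explanation; if it is not, the contrast is the report plus tailoring. No extra items are needed, since every participant receives both by the end of the study. The cost is nevertheless more than a change of timing. The comparator becomes verbal OHI plus leaflet and mirror, so Aims, Primary Objectives and the arm labels must be reworded along with the Visit 1, Visit 2 and items sections. Under the Independent Ethics Committee section, such an amendment goes through sponsor review and then to the ethics committee.
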